9.2 SETTING

An anonymized dataset from the cooperating sickness funds, which includes all patients with at least one COPD diagnosis, who were insured by this sickness funds for the entire period (01/01/2013 - 30/06/2018) will be available.

A patient will be confirmed as being COPD-incident if specialists documented at least two confirmed outpatient COPD diagnoses (ICD J44.-) and/or at least one inpatient COPD diagnosis (ICD J44.-), without such diagnoses in the previous 12 months and without any COPD prescription in the previous 12 months (Suppl. Table 2).

Specific inclusion criteria can be described as follows:

- All patients should have been covered by the sickness fund for the entire period (01/01/2013-30/06/2018) or, in case a patient deceased after index date, for the time until death
- A patient will be included as an incident COPD patient if either a hospital documented at least one COPD diagnosis (ICD-10 J44.-) or a specialist (pneumologist) documented at least two confirmed COPD diagnoses (above ICD-10 code) in two different quarters; the first of the above diagnoses is defined as index diagnosis; inclusion period is defined as lasting from 01/01/2014 until 30/06/2017

- Patients should not have received any COPD diagnosis (ICD-10 J44.-) or any COPD-associated medication (Suppl. Table 2)⁹ in the 12 months pre-index period
- Patient should have, at date of incident COPD diagnosis (index date), an age of at least 40 years

Patients who received at least one confirmed inpatient asthma diagnosis or two confirmed outpatient diagnoses of asthma (ICD-10: J45.-) by pneumologists after the incident COPD diagnosis (index diagnosis) will be separately observed.

Based on these inclusion/exclusion criteria, the following data sets will be analyzed (Figure 3)¹⁰:

- COPD-FULL DATA: All incident COPD patients with a follow-up of up to 54 months
- COPD-12: All incident COPD patients with a follow-up¹¹ of 12 months since index date
- COPD-24: All incident COPD patients with a follow-up of 24 months since index date
- COPD-36: All incident COPD patients with a follow-up of 36 months since index date
- COPD DMP-FULL DATA: All incident COPD patients with available DMP data (at least one entry during 3 months after index date¹²) and a follow-up of up to 54 months.
- COPD DMP-12: All incident COPD patients with available DMP data (at least one entry during 3 months after index date) and a follow-up of 12 months since index date
- COPD DMP-24: All incident COPD patients with available DMP data (at least one entry during 3 months after index date) and a follow-up of 24 months since index date
- COPD DMP-36: All incident COPD patients with available DMP data (at least one entry during 3 months after index date) and a follow-up of 36 months since index date.

⁹ Prescription of systemic/oral corticosteroids (SCS/OCS) will not be considered as exclusion criteria

¹⁰ Please note that this samples will not include patients with at least one confirmed inpatient or two confirmed outpatient diagnoses of asthma (ICD-10: J45.-) by pneumologists after the incident COPD diagnosis (index diagnosis) during the follow-up period. Those patients will be described separately.

[figure not shown]
¹¹ Time since patient-individual index date until 30/06/2018; patients who died within this period will not be excluded from the analysis

¹² So far it is unknown how many patients were included in the DMP directly after incident diagnosis and for how many patients an entry in the first months after diagnosis will be available. Thus, depending on the pattern that will be observed in the data, the restriction „at least one entry during the 3 months after index date“ might be extended to „at least one entry during the 6/12 months after index date“.

Figure 3

Baseline period, inclusion period, follow-up period for different study samples

(note: for time to event analyses, COPD-full data sample (with full follow-up times) will be applied). DMP: disease management program (refers to the subsample of patients who participate in the COPD DMP and thus provide more detailed data)

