7. RATIONALE AND BACKGROUND

In terms of chronic obstructive pulmonary disease (COPD) drug therapy, the current German COPD guideline (S2) [1] recommends a treatment escalation procedure (Figure 1). For incident COPD patients (for the sake of simplicity, newly diagnosed and so far treatment naïve COPD patients will be referred to as “incident COPD patients” in the following), the guideline recommends the following:

- No treatment (low symptom burden) or
- Short-acting beta antagonist (SABA) or short-acting muscarinic antagonist (SAMA) or
- Long-acting beta agonist (LABA) or long-acting muscarinic antagonist (LAMA) or LABA+LAMA.

All other treatments, particularly combination treatments including inhaled corticosteroids (ICS), are only recommended as escalation therapy. However, despite the increasing evidence (e.g. WISDOM study [3], FLAME study [4]), there might exist the view that early use of ICS in the treatment of COPD might be advisable, and might be prescribed in a substantial percentage of COPD-incident patients.

Figure 1 Treatment recommendations with regard to COPD stages, according to German 2018 S2 guideline [1]

Medikamentöse Dauertherapie der COPD	
Symptome - Ausmaß der Lungenfunktions-einschränkungen berücksichtigen	Medikamentöse Therapie
Wenig (z. B. CAT < 10) GOLD Gruppe A	- Keine - SABA + SAMA (initial) - LABA oder LAMA
Viel (z. B. CAT \geq 10) GOLD Gruppe B	- LABA oder LAMA - LABA + LAMA
Exazerbationen > 1 oder Exazerbation mit Hospitalisierung GOLD Gruppen C und D	
Nicht vorbehandelt	LAMA oder LAMA + LABA
Vorbehandelt	LAMA + LABA
Eskalation/Wechsel	 LABA + ICS → LAMA + LABA + ICS
	\pm Roflumilast (Phänotyp chronische Bronchitis)

Currently, knowledge on real world treatment of incident COPD patients in Germany is sparse, in particular regarding the frequency of different drug therapy prescriptions and the frequency of early therapy escalation including ICS. With the current analyses, we aim to emphasize the central role of LAMA/LABA therapy in COPD and importance of treatment guideline adherence.

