9. RESEARCH METHODS

9.1 STUDY DESIGN

A retrospective analysis will be done based on a claims dataset delivered by two German sickness funds (so far, a cooperation with [REDACTED] is planned, second sickness fund needs to be named yet). The dataset will cover the period 01/01/2013-30/06/2018⁷. In selected analyses, incident COPD patients will be observed for an exact follow-up period of 12 months (in subgroup analyses: 24 and 36 months); censoring of patients will only be done in case a patient died during the respective follow-up period. [REDACTED]

The data will be analyzed for a pre-index period (12 months before index diagnosis) and for a follow-up period of 12 months after index date. In subgroup analyses, longer follow-ups (24 and 36 months, and full observation time (up to 54 months⁸)), are used. Death after index diagnosis during the follow-up is the only accepted exception from this rule. For a subsample of patients, disease management program (DMP) data might be available. These provide disease specifics such as forced expiratory volume in 1 second (FEV₁) values, specifics of prescribed therapy, and exacerbation frequency and severity.

The dataset contains available information on the sociodemographic characteristics of the patients, their treatment with prescription aids and medications, their outpatient and inpatient treatment, and COPD-specific clinical parameters for the patients who participated in a disease management program (DMP). A first overview of data generally available in claims data of a German sickness fund is given in Table 1. The study-specific data set (required data according to approved study protocol) needs to be approved by the respective sickness funds, based on the study objectives and the respective methodology as outlined in this protocol.

⁷ If more data will be available until time of analysis start, further quarters (from 2018) will be included into the analysis.

⁸ If more data will be available until time of analysis start, further quarters (from 2018) will be included into the analysis.

[figure not shown]
Table 1 Data generally available in the claims data set

Sociodemographic characteristics	Inpatient care	Outpatient care	Outpatient medication (prescriptions only)	Other data

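### Incidence is checked over only 12 months before index although the dataset holds 12 to 54, and no visible analysis tests whether the treatment called initial really is

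*Combined protocol and SAP*

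**What the plan says.** Section 7 and the abstract use the term incident for "newly diagnosed and so far treatment naïve COPD patients". Section 9.2 puts this into practice with a summary sentence, which requires that the patient be "without such diagnoses in the previous 12 months and without any COPD prescription in the previous 12 months (Suppl. Table 2"), and with a formal criterion. The criterion is the stricter text: it bars any J44 code from any provider, and any drug in Supplemental Table 2 except systemic steroids, "in the 12 months pre-index period".

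Section 9.1 limits the history in the same way: "The data will be analyzed for a pre-index period (12 months before index diagnosis) and for a follow-up period of 12 months after index date". On the index date, section 9.2 says that "the first of the above diagnoses is defined as index diagnosis; inclusion period is defined as lasting from 01/01/2014 until 30/06/2017". On insurance it says: "All patients should have been covered by the sickness fund for the entire period (01/01/2013-30/06/2018"), with death after index as the only exception.

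The legible text has no longer look-back, no sensitivity analysis on its length, and no mention of the issue under limitations (9.9) or bias (9.12). The nearest text is a footnote in the abstract: the Steering Board may discuss adding 2010 to 2012 data, which would need ministry approval. No purpose is given.

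**The concern.** COPD is chronic, and coding or prescribing can lapse for a year. Take a patient with GP J44 codes and a LABA+ICS inhaler in 2013 to 2015, nothing for just over a year, and then pneumologist codes in 2017. This patient enters as newly diagnosed and treatment naive although the study's own data show otherwise.

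Several results depend on the index treatment being the first one: the first-line column and the cascades of Table 2, the Kaplan-Meier times from incident diagnosis to dual and triple therapy, and the guideline comparison. That comparison scores any ICS at index as outside both guidelines, and a LABA/LAMA combination at index as outside the 2012 guideline. Prior treatment matters to the guideline itself: Figure 1 separates untreated from pre-treated patients in GOLD groups C and D and places ICS combinations under escalation or switch. A returning patient scored as a starter may be judged against the wrong row.

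**Working it through.** **Inputs.** Data from 01/01/2013 to 30/06/2018 (9.1); index dates from 01/01/2014 to 30/06/2017 (9.2); look-back rule 12 months (9.2); expected cohort above 40,000 (9.5), taken here as 40,000. Section 9.2 counts follow-up from index to 30/06/2018, which sets the last index date for each sample.

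**The plan's own figure.** Section 9.2 gives "COPD-FULL DATA: All incident COPD patients with a follow-up of up to 54 months". From 01/01/2014 to 30/06/2018 is 54 months, so it reproduces. That is follow-up. The maximum look-back, from 01/01/2013 to 30/06/2017, is also 54 months, but it is a different quantity.

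**History on file.** Look-back = index date minus 01/01/2013. The plan gives no distribution of index dates, so I assume a uniform one. Mean look-back = (minimum + maximum)/2. Unused = mean − 12. Share with at least w months = (maximum − w)/(length of index window).

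| Sample | Last index | Window (months) | Look-back (months) | Mean | Unused | At least 24 | At least 36 |
|---|---|---|---|---|---|---|---|
| COPD-12, full data | 30/06/2017 | 42 | 12 to 54 | 33 | 21 | 30/42 = 71% | 18/42 = 43% |
| COPD-24 | 30/06/2016 | 30 | 12 to 42 | 27 | 15 | 18/30 = 60% | 6/30 = 20% |
| COPD-36 | 30/06/2015 | 18 | 12 to 30 | 21 | 9 | 6/18 = 33% | 0% |

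Of 40,000 patients, about 28,600 (40,000 × 30/42) would have at least 24 months of history and about 17,100 (40,000 × 18/42) at least 36.

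**Does the index definition close the gap?** If the first qualifying diagnosis means the first in the whole dataset, earlier qualifying hospital or pneumologist diagnoses are caught. Earlier GP codes, a single pneumologist code and earlier drugs are not. The gap remains under either reading.

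**Illustration of size (assumed inputs, not from the documents).** Let a share c of the cohort have an older record, and let their initial ICS use differ by d from that of new patients. The reported share then moves by c × d.
- c = 2%, 5%, 10%, 20% means 800, 2,000, 4,000, 8,000 of 40,000 patients.
- With 20% ICS use in new patients and 40% in returning ones, d = +20 points. The reported share becomes 20.4%, 21%, 22%, 24%.
- With d = −20 points it falls by the same amounts: 0.4, 1, 2, 4 points.
- For scale, the 95% CI half-width at 20% and n = 40,000 is 1.96 × √(0.20 × 0.80/40,000) = 0.0039, about 0.4 points. A shift of 1 point would exceed the reported uncertainty.

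**The case against.** The strongest reply is that 12 months is the longest look-back available equally for every index date, and that the plan applies it consistently. An all-available look-back as the main rule would make incidence depend on calendar time, with a mean washout of 33 months in COPD-12 and 21 in COPD-36. Washout length would then be mixed with follow-up length across the 12/24/36-month results. This stands, and the main definition should not change.

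It also stands that one old prescription does not prove earlier COPD. Supplemental Table 2 includes short-acting drugs and codes outside R03 (R01AD01, R01AD05, R01AD08, R01AX03), although the abstract describes COPD medication as R03. A longer window would remove some genuinely new patients, and more of them at later index dates.

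A 36-month run cannot serve every sample: it is empty for COPD-36, and for COPD-24 it rests on index dates from January to June 2016 only.

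Parts of 9.1, the section after 9.7.1 and part of Table 4 are blacked out, and Figure 3 is not shown. A look-back sensitivity analysis in the hidden text cannot be ruled out.

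None of this answers the narrower point: complete history will be on file, and no legible passage uses it to check the label placed on the cohort.

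**Conclusion.** The point holds as a gap in sensitivity analysis. The 12-month rule is not an error. Patients whose last J44 code or listed drug lies more than 12 months before index are counted as newly diagnosed and treatment naive, although 12 to 54 months of complete history will be on file. The averages of 33, 27 and 21 months rest on uniform index dates; the ranges do not.

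A reader might infer that the rule inflates early ICS use and so favours the expectation in section 7 that ICS is often started early. The documents do not support that. They give neither the number of returning patients nor their treatment. Such patients may restart at a higher step, or they may have mild disease and restart low or untreated. A reader might also take 54 months as typical; it applies only to patients indexed at the very end of the window.

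**What to change.** Keep the uniform 12-month rule as the main definition and add to sections 9.2 and 9.7:

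1. Report how many included patients have any J44 code or Supplemental Table 2 drug between 01/01/2013 and the start of the 12-month window. Except systemic steroids, as now, and show R03 codes separately from R01 codes.
2. Sensitivity analysis (a): exclude those patients, using all available history.
3. Sensitivity analysis (b), fixed longer look-back:
   - 36 months (index from 01/01/2016, about 43% of patients before exclusions) for COPD-12 and the index-date guideline comparison;
   - 24 months (index from 01/01/2015) for COPD-12 and COPD-24.
4. State that for COPD-36 the 24-month run covers only index dates from January to June 2015, about 5,700 patients (40,000 × 6/42) before exclusions, and that the 36-month run is impossible. These limits move if further 2018 quarters are added.

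The data are already requested, so the cost is smaller samples in the added runs and a little more analysis work. In (a) the look-back still varies with index date; the fixed runs in (b) remove that variation. If the results do not move, the label is supported. If they do, the report should say so beside the main results.

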9.3.2 Outcomes

9.3.2.1 Primary outcomes

The primary objective of this study is to describe the real-life drug treatment of patients with incident COPD, including description of treatment sequence/escalation in the first 12/24/36 months after incident diagnosis. This analysis will be based on the following samples:

- COPD-12: All incident COPD patients with a follow-up of 12 months since index date (analysis will be done for the first 12 months of observation)
- COPD-24: All incident COPD patients with a follow-up of 24 months since index date (analysis will be done for the first 24 months of observation)
- COPD-36: All incident COPD patients with a follow-up of 36 months since index date (analysis will be done for the first 36 months of observation)
- COPD FULL DATA: All incident COPD patients. (analysis will be done for the full observation period)
- COPD DMP-12: All incident COPD patients with available DMP data (at least one entry after index date) and a follow-up of 12 months since index date (analysis will be done for the first 12 months of observation)

In this analysis, baseline treatment as well as treatment cascades including mean duration of treatment in the pre-defined follow-up periods will be assessed. Results will be reported as follows:

- Mean number of different agents an observed patient received (per patient year)¹³
- List of most frequently prescribed agents (based on [Suppl. Table 2](#)) including percentage of patients who received these agents
- Longitudinal analysis of treatment patterns/cascades with long-acting bronchodilators and ICS, as described in [Table 2](#). Here, proportion of observed patients whose treatment can be described by the pre-defined treatment patterns will be assessed.

Table 2

Description of treatment patterns/cascades (template for reported outcomes)^{14,15}
(please note: below table might not show all theoretically possible treatment patterns. In the analysis, based on observed treatment patterns, all treatment pattern combinations that were observed in >5% of the patient population will be reported)

Therapy pattern after index date	1st line	2nd line	3rd line	4th line	N (%) of patients
Mono, no switch during follow-up period	LAMA	-	-	-	...
	LABA	-	-	-	...
	ICS	-	-	-	...
Mono, with switch	LAMA	LABA	-	-	...
	LAMA	ICS	-	-	...
	LABA	LAMA			
	LABA	ICS			
	ICS	LABA			
	ICS	LAMA			

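### No maximum gap between the two pneumologist codes: patients have 12 to 54 months to qualify depending on index date, and the time between codes is death-free on that route

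*Combined protocol and SAP*

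**What the plan says.** Section 9.2 (repeated in the abstract) gives two routes into the cohort. The hospital route needs one inpatient J44 code. The outpatient route applies when a pneumologist has "documented at least two confirmed COPD diagnoses (above ICD-10 code) in two different quarters; the first of the above diagnoses is defined as index diagnosis". Neither place limits the interval between the two codes.

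The "inclusion period is defined as lasting from 01/01/2014 until 30/06/2017". Section 9.1 has the data ending on 30/06/2018 and gives "full observation time (up to 54 months" as the maximum. Follow-up is defined in a footnote to 9.2 as "Time since patient-individual index date until 30/06/2018; patients who died within this period will not be excluded from the analysis". The Figure 3 note says that "for time to event analyses, COPD-full data sample (with full follow-up times) will be applied", and 9.3.2.1 counts Kaplan-Meier time from the incident diagnosis.

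The limitations (9.9) do not mention the point. Section 9.12 discusses region, continuous insurance and demographics only. The ENCePP checklist ticks time-related bias as addressed in 9.11, but 9.11 says nothing on it.

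**The concern.** Two features of the outpatient rule interact with the data cut.

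First, the opportunity to qualify is unequal. A patient first coded in early 2014 and again in early 2018 enters with a 2014 index. A patient with the same attendance pattern first coded in mid-2017 would get the second code after the data end and is not included on this route. The 12-, 24- and 36-month samples are cut by index date, so they differ in how long their members had to qualify. Results on treatment, exacerbations and cost will be set side by side across these samples, and part of any difference could come from this selection.

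Second, the index precedes the event that confirms eligibility. On the pneumologist route a patient must be alive at the second code, so no death can fall between the codes. The plan otherwise keeps deaths after index on purpose. Early deaths, and the hospital use and cost that go with them, are therefore under-counted on this route but not on the hospital route.

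**Working it through.** **Inputs from the protocol.** Index dates 01/01/2014 to 30/06/2017 (9.2); data end 30/06/2018 (9.1); index at the first code and no maximum gap (9.2); deaths kept (9.2, footnote 11).

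**1. The plan's own figure.** From 01/01/2014 to 30/06/2018 is 54 months, which reproduces 9.1. From 30/06/2017 to 30/06/2018 is 12 months.

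**2. Time to qualify, by sample.**
- COPD-36: index 01/01/2014 to 30/06/2015, so 36 to 54 months.
- COPD-12: all index dates, so 12 to 54 months. It contains every COPD-36 patient.

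Other readings change the figures but not the problem. If both codes had to fall in the inclusion period, the range would be 0 to 42 months. If data were extended to 31/12/2018 (9.1 says that "further quarters (from 2018) will be included into the analysis" if available), it would be 18 to 60. If the 2013 to 2017 period named in 9.4 applied, it would be 6 to 48.

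**3. Illustration of the composition effect.** All of these inputs are assumed: time to second code is exponential with rate r per year; a share w of first-coded patients are sparse attenders (w = 15% or 30%, r = 0.2 or 0.4); the rest have r = 3; index dates are uniform; pneumologist route only; deaths and the different-quarter rule are ignored.

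The probability of qualifying, averaged over windows from a to b years, is A(r) = 1 − [exp(−ra) − exp(−rb)] / [r(b − a)].

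At r = 0.3, COPD-36 gives 1 − (0.4066 − 0.2592)/0.45 = 67%, and COPD-12 gives 1 − (0.7408 − 0.2592)/1.05 = 54%.

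The sparse share among qualifiers is w·A(r) / [w·A(r) + (1 − w)·A(3)]. For w = 15% and r = 0.2:
- COPD-36: 0.15 × 0.526 / (0.15 × 0.526 + 0.85 × 1.000) = 8.5%.
- COPD-12: 0.15 × 0.411 / (0.15 × 0.411 + 0.85 × 0.995) = 6.8%.

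| w | r | COPD-36 | COPD-12 | Gap (points) |
|---|---|---|---|---|
| 15% | 0.2 | 8.5% | 6.8% | 1.7 |
| 15% | 0.4 | 12.0% | 10.2% | 1.8 |
| 30% | 0.2 | 18.4% | 15.0% | 3.4 |
| 30% | 0.4 | 24.9% | 21.6% | 3.3 |

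**4. Illustration of the death-free interval.** The shortest possible gap is one day (31 March and 1 April) and the longest about 54 months. Assume exponential death (monthly hazard d) and exponential time to second code (hazard h), with no entry through hospital. Twelve-month mortality among those who qualify within W ≥ 12 months is

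[(1 − e^(−12d)) − d/(d+h)·(1 − e^(−12(d+h)))] / [h/(d+h)·(1 − e^(−W(d+h)))].

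Take an assumed true mortality of 6% (d = 0.00516) and a median gap of 6 months (h = 0.1155). The numerator is 0.060 − 0.0427 × 0.765 = 0.0273. The denominator is 0.957 × 0.765 = 0.732 for W = 12 and about 0.956 for W = 54. The results are 3.7% and 2.9%.

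For median gaps of 3, 6 and 12 months the figures are 4.3%, 3.7% and 3.4% with a 12-month window, and 4.0%, 2.9% and 1.9% with a 54-month window. With true mortality of 3% or 10%, the ranges over both windows are 0.9% to 2.1% and 3.2% to 7.2%.

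**5. After a common 12-month limit.** The window is 12 months for every index date, and the last one closes on 30/06/2018. The composition effect of unequal windows disappears. The W = 12 figures in step 4 show that the death-free interval does not.

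**The case against.** The strongest reply concerns size and use. The study is mainly descriptive, and no test between the 12- and 36-month samples is planned. The one visible comparison across years, cost in year 1 against years 2 and 3, is made within COPD-36, so differing sample composition cannot confound it. If nearly all patients are recoded within a year, the window effect almost vanishes. Hospital-indexed patients need no second code and dilute it further. All of this stands, and it keeps the point at the level of a cheap improvement.

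Three stronger readings are tempting but not supported.

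- A reader might compare COPD-36 with patients indexed 07/2016 to 06/2017. On the same assumptions that gives 67% against 36% qualifying at r = 0.3, and sparse shares of 8% to 25% against 4% to 16%. That last index year is not an analysis sample. COPD-12 spans all index dates, and the contrast between planned samples is the smaller one above.
- A reader might infer that anyone who dies after a single pneumologist code is lost. An inpatient J44 diagnosis qualifies a patient by itself, so the loss concerns those without one. Section 9.2 does not say which code is then the index.
- A reader might infer that the patients added by a longer window have milder or doubtful disease. The documents contain nothing on this.

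The reply does not reach the rule itself. No visible text limits the gap, and the inclusion criteria appear in full in two places.

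**Conclusion.** The point holds as a specification gap of modest size. It follows from the dates alone that time to qualify runs from 12 to 54 months, that COPD-36 and COPD-12 differ in this respect, and that the interval between codes is death-free on the pneumologist route.

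The size is not computable, because the documents give no distribution of gaps, no mortality and no split by route. On the assumed inputs, the sparse-attender share differs by 1.7 to 3.4 percentage points between COPD-36 and COPD-12 on the pneumologist route, and by less once hospital-indexed patients are added.

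The death-free interval may matter more for exacerbation, resource-use and cost results: under the assumptions in step 4, observed 12-month mortality falls clearly below the true value even with a 12-month window. Those figures are illustrations and ignore entry through hospital. The change is worth making because it is cheap and can be observed for every index date.

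**What to change.** In 9.2, and in the abstract, require the second confirmed pneumologist diagnosis, in a different quarter, within 12 months of the first for every patient. This is fully observable for the last index date, provided the data run to 30/06/2018; the different period in 9.4 should be reconciled with 9.1.

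Add a sensitivity analysis that starts exacerbation, resource-use and cost, and time-to-event follow-up at the confirming diagnosis for the pneumologist route. Membership of the fixed-length samples then has to be judged from that date, since a patient confirmed in mid-2018 has almost no follow-up left.

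Do not let a later hospital J44 diagnosis confirm the first pneumologist code in the main analysis. Hospitalisation is itself an outcome, and such patients would enter because they had the event.

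The cost is one sentence in two places, one extra run, and the patients whose second code comes after more than 12 months. Their number is unknown and should be shown in the planned attrition chart. Under the assumptions of step 3, sparse attenders would be retained with probability 1 − exp(−r), that is 18% at r = 0.2 and 33% at r = 0.4, so the loss in that group could be large.
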